Interviews will seek to understand the perceived acceptability, benefits, concerns or harms associated with starting LLT and how these may impact adherence, considering the variation in the ages participants started LLT. Interviews will also cover treatment and monitoring experiences and views on service provision and access, and how these could be improved. Questionnaires and interviews will inform information needs for patients and families.

Target recruitment is increasing the Register to 1,374 paediatric FH patients with clinical data entry, 500 participants for questionnaires and 40 participants for interviews. Clinical, questionnaire and interview consent forms and data collected will be securely stored at the University of Nottingham.

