6.1.5 Recruitment and consent procedure

Patients are recruited for clinical data collection by clinicians (or a nominated staff member who will usually be a clinical member of staff with experience of working with the patient group) at NHS clinical sites seeing individuals diagnosed with FH during childhood across England and Wales. The clinician or nominee will inform the participant and/or their parent/guardian, of all aspects pertaining to participation in the study. The clinical setting is chosen for base recruitment as data collection is from clinical records and consultations with health professionals. Patients or their parents/guardians are initially approached for recruitment during or between clinic visits, via email, telephone, text message or post, based on accepted recruitment practices and patient-contact methods within the clinical site. Clinical teams also have the option of using trained NHS research volunteers who will be approved by the site PI to assist in recruiting participants. The research volunteers will have lived experience of FH in their family or undergo training paediatric FH. It is possible for patients or parents/guardians to approach their clinicians with interest in participating in the study; their clinical team will need to have been approved for data collection prior to recruitment.

Patients aged 16 years and over or parents/guardians of younger patients are recruited for questionnaire data collection if they express an interest in being contacted for participation in further research when they enrol for clinical data collection. The study team at the University of Nottingham will directly contact individuals who express an interest in further research to invite them to participate in questionnaire data collection.

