Analysis: Interview audio data will be transcribed verbatim. Data will be analysed using the framework approach, which is a hierarchical, matrix-based method developed for applied research.³⁷ The framework will enable us to map thematic differences/similarities within and between groups, such as by age at LLT initiation or adherence. Data will be coded both according to a priori themes and inductively. Initial readings will facilitate familiarisation and will lead to the generation of codes. Further analysis will result in more substantive themes and sub-themes (the analytical framework). Data will then be indexed according to the analytical framework. A sub-sample of data will be double coded to ensure validity of interpretations. We will also incorporate respondent validation whereby young people and parents will be invited to check initial accuracy of transcripts, add to them after a period of reflection, and review whether mapped themes are a reasonable reflection of their data. Finally, themes will be discussed and agreed between the research team, allowing clarification of the final framework that will then be applied across all transcripts.

The collected qualitative data will complement and clarify the quantitative findings by helping to identify common themes, and possible explanations.

Outputs

- Identification of barriers and facilitators to treatment adherence considering the role of age at initiation, access to care/monitoring and triangulation with questionnaire findings (e.g., accounting for differences according to demographics)
- Identification and description of the information needs for starting LLT at different ages and how these maybe met
- Triangulation of findings from questionnaire and interviews with children, young people, parents and healthcare professionals to propose recommendations for how to best implement health service provision for treatment initiation and monitoring.

7.5 Objective 5: Estimate the impact of initiating LLT at different ages on the costs of managing FH over the short-term in children and young people

Method: To inform the cost-effectiveness model (Objective 6), we will estimate NHS costs of managing CYP with FH and the effect of starting LLT on costs using data on healthcare use (e.g., outpatient appointments, GP visits) **collected from PFHR patient questionnaires and HCP questionnaires**, as the preferred option for capturing most FH secondary care and a common method used in trials.²⁴

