Analysis: Using information on resources required during appointments (e.g. personnel, duration, tests) collected via the PFHR patient questionnaires and HCP questionnaires and national unit costs,³⁸ we will calculate total healthcare costs per individual. We will estimate the impact of starting LLT on NHS costs over time, accounting for potential confounders. Our analysis approach to confounding and missing data will be similar to that described in Objective 1(a), using an appropriate model to accommodate the typically skewed cost data (e.g., generalised linear models).³⁹

Outputs

- Estimates of the use of NHS services by CYP with FH and their related costs
- Estimates of the effect of starting LLT on NHS costs related to service use

7.6 Objective 6: Estimate long-term health outcomes and NHS costs of starting LLT at different ages and LDL-C thresholds to identify a cost-effective approach to management

Method: To identify the cost-effective approach to initiating LLT at a range of ages and LDL-C thresholds, we will develop a new cost-effectiveness model. A decision model is required to estimate long-term reductions in CVD risk (which cannot be observed without decades of follow-up), given observed shorter-term LDL-C reductions. We will take the NHS perspective and express health outcomes primarily in quality-adjusted life years (QALYs). We will collaborate with the CYPAG, PCAG and clinical specialists to capture outcomes that matter to patients, families, clinicians, and healthcare commissioners. The cost-effectiveness analysis will be conducted and reported in accordance with current methodological guidance for cost-effectiveness analysis.⁴⁰

Analysis: The model structure will be based on our model developed to analyse the cost-effectiveness of alternative cascade screening protocols for FH.²⁵ We will link LDL-C to CVD risk based on the wellestablished concept that LDL-C increases CVD risk and this effect increases over time.¹⁷ Hence, the same LDL-C reductions over longer periods (from earlier LLT initiation) result in greater CVD risk reductions and more CVD events avoided. We will account for the impact of adherence in terms of its impact on LDL-C reductions from LLT (which are inherent to the estimates from the PFHR and CPRD data analyses) and via the proportion of CYP who continue LLT use into adulthood (estimated in Objective 3).

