	[name],
	[name]
	[name]
	[contact]
	Email: [contact]
Study Coordinating Centre:	School of Medicine
	[name],
	[name]
	[name]

Page 2 of 37

Paediatric FH Register Study Protocol IRAS ID: 324246 18 June 2024 Final version 2.0

SYNOPSIS

Title		
Title	ESTIMATING APPROPRIATE LIPID LOWERING	
	MANAGEMENT IN THE UNITED KINGDOM	
	PAEDIATRIC FAMILIAL HYPERCHOLESTEROLAEMIA	
-	REGISTER PFHR	
Acronym	PFHR	
Short title	Paediatric FH Register Study	
Chief Investigator and	[name]	
Study Lead		
Co-Investigator and	[name]	
Study Co-Lead		
Objectives	To collect clinical data on individuals diagnosed with	
	familial hypercholesterolaemia during childhood (data held	
	in a Paediatric Familial Hypercholesterolaemia Register),	
	in combination with questionnaires and qualitative	
	interviews, to answer the following questions:	
	What are the health benefits and risks in the short-	
	term and longer-term to monitoring health and starting	
	treatment (mainly cholesterol-reducing medications) at	
	different ages and cholesterol concentrations during	
	childhood and adolescence among people diagnosed	
	with familial hypercholesterolaemia (also called clinical	
	effectiveness)?	
	For children and young people diagnosed with familial	
	hypercholesterolaemia and their families, what is the	
	acceptability of monitoring health and starting	
	treatment (mainly cholesterol-reducing medications) in	
	childhood and adolescence?	
	 How does following health monitoring and taking 	
	treatment medications as directed by health services	
	(also called adherence) vary across childhood and	
	adolescence and what are the short-term and longer-	
	term health benefits and risks related to variation?	
	How do health service costs of clinical familial	
	hypercholesterolaemia monitoring and treatment in	
	childhood and adolescence balance with the savings	
	produced by preventing early heart disease in longer-	
	term and does this provide value for money (also	
	called cost-effectiveness)?	
Study Configuration	Multi-centre across England and Wales	
0		
Setting	Secondary care sites providing clinical care for paediatric	
	familial hypercholesterolaemia	
Number of	Over the next 5 years, 1,000-2,000 individuals with familial	
participants	hypercholesterolaemia diagnosed during childhood will be	
	recruited for clinical data collection. 400-500 of these will	

Page 3 of 37

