This is descriptive research using the available paediatric patient population diagnosed with FH across the United Kingdom (except Scotland). Based on estimates of paediatric patients with FH currently being seen and newly presenting patients at clinical sites contacted by the Study Leads, we estimate at least 1,300 patients with clinical data entry on the PFHR over the next 5 years. Clinical sites will be contracted and funded for recruitment.

We estimate 400-500 participants with questionnaire data and 40 participants with interview data.

Page 24 of 37

Paediatric FH Register Study Protocol IRAS ID: 324246 18 June 2024 Final version 2.0

It is acknowledged that FH is currently underdiagnosed in the general population, however, cascade testing aims to increase earlier diagnosis. Based on currently available estimates from mid-2020²⁷, the general population age 0-19 years is 13,330,355 in England, 701,777 in Wales, and 484,495 in Northern Ireland. At an estimated paediatric FH prevalence of 0.28% in the UK,⁴ there are potentially 37,325 children living with FH in England, 1,964 in Wales, and 1,356 in Northern Ireland.

ADVERSE EVENTS

The occurrence of an adverse event as a result of participation in this study is not expected. There is no participation in any interventions as a result of participation in this study. Participation will have no consequences to an individual's clinical care.

ETHICAL AND REGULATORY ASPECTS

There are no interventions, separate clinical visits nor measurements required for participation in the study, beyond the patient's usual NHS clinical follow-up. Participation in the study involves consent for the patient's NHS clinical care information to be collected by the patient's clinical team for the study with the option for the patient or their parent/guardian to fill out questionnaires of self-reported information about their experience of FH, and the option of participating in an interview about their experience of FH.

Patients will be provided with contact details for the Study Management Team to discuss any concerns relating to participation and will be directed to discuss any personal clinical concerns with their FH clinical care team or general practitioner.

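### Patient-questionnaire costs and self-reported adherence levels come from families who opt in twice, and the stated weighting and imputation are not said to reach those who never join

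*Protocol*

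**What the plan says.** **Entry.** Under Protocol 6.1.5, questionnaires are offered to patients or parents "if they express an interest in being contacted for participation in further research" at enrolment for clinical data. A separate consent follows. The Appendix (Recruitment, phase b) approaches everyone who expressed interest. A sampling framework that seeks diversity is described for the interviews only.

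**Numbers.** Section 6.1.1: "Target recruitment is increasing the Register to 1,374 paediatric FH patients with clinical data entry, 500 participants for questionnaires and 40 participants for interviews". Appendix, Sample size and justification: "we estimate at least 1,300 patients with clinical data entry on the PFHR over the next 5 years" and "We estimate 400-500 participants with questionnaire data and 40 participants with interview data". The Appendix synopsis gives "1,000-2,000 individuals with familial" hypercholesterolaemia for clinical data. The abstract puts the existing Register at 613.

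**Costs.** Section 7.5 bases NHS costs on healthcare use "collected from PFHR patient questionnaires and HCP questionnaires". On method it says: "Our analysis approach to confounding and missing data will be similar to that described in Objective 1(a"). Section 7.1, Analysis (a), lists what that means: treatment weights to balance exposed and unexposed children, censoring weights for non-adherence and loss to follow-up, and multiple imputation of LDL-C outcomes and confounders. The Section 7.6 input table takes the cost of managing treated and untreated children from these results.

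**Adherence.** Section 7.3 analyses questionnaire adherence at baseline, 8, 16 and 24 months descriptively and then by GEE on a list of covariates. No step for selection into the questionnaire is given.

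**The concern.** Families who volunteer twice may differ from the rest of the Register in the very things the questionnaire measures: how often they attend and how well they take treatment. The methods named for Objective 5 act on confounding between treated and untreated children, on drop-out, and on missing values. None is said to act on who enters the questionnaire in the first place.

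The stakes are highest for cost. Section 5.1 explains that outpatient appointments are expected to be the largest cost driver and are not consistently recorded in CPRD, which is why questionnaires are used. If the sample attends more than the Register as a whole, the cost per child passed to the economic model is too high. If it adheres better, the reported level of self-reported adherence is too high.

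**Working it through.** **1. Share of the Register that answers.** The 500 has no derivation in the protocol, so there is no formula to reproduce; only ratios of stated targets can be formed.

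- Section 6.1.1 targets: 500/1,374 = 36.4%. With the Appendix lower figure: 400/1,374 = 29.1%.
- Appendix Register size: 400/1,300 = 30.8% to 500/1,300 = 38.5%.
- Synopsis range as denominator: 400/2,000 = 20% to 500/1,000 = 50%.
- If only the added patients can be invited: 1,374 - 613 = 761; 400/761 = 52.6% to 500/761 = 65.7%.

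**2. Error in an unweighted mean number of appointments.** Let p be the share joining, the non-joiner mean be 1 and the joiner mean 1 + d. The mean over all patients is 1 + pd, so the relative overstatement is (1 + d)/(1 + pd) - 1 = d(1 - p)/(1 + pd). The value of d, and its sign, are assumptions. For example, p = 0.364 and d = 0.2 give 1.2/1.073 = 1.12.

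| p | d = 0 | d = 10% | d = 20% | d = 30% |
|---|---|---|---|---|
| 29.1% | 0 | 6.9% | 13.4% | 19.6% |
| 36.4% | 0 | 6.1% | 11.9% | 17.2% |
| 52.6% | 0 | 4.5% | 8.6% | 12.3% |
| 65.7% | 0 | 3.2% | 6.1% | 8.6% |

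**3. Effect of LLT on cost.** Suppose the true means for joiners are a + c (treated) and b + c (untreated), and for non-joiners a and b. The joiner difference is a - b, so the extra use c cancels. If the extra use is instead proportional, and participation is equal in both groups, the joiner difference is (1 + d)(a - b) against (1 + pd)(a - b) overall. The overstatement is then the same percentage as in the table.

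**4. Level of self-reported adherence.** The excess is (1 - p) x (joiner level - non-joiner level). Assume 80% of joiners are highly adherent and 75%, 70%, 60% or 50% of non-joiners. At p = 36.4% the excess is 3.2, 6.4, 12.7 or 19.1 points; at p = 29.1% it is 3.5, 7.1, 14.2 or 21.3. The 95% half-width at n = 500 is 1.96 x sqrt(0.8 x 0.2/500) = 3.5 points, so at these shares even the smallest assumed gap is about as large as the sampling error.

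**5. Can it be corrected?** The Appendix (Study forms) gives each participant one identity code across the clinical and questionnaire platforms. The Register also supplies age, site, deprivation, ethnicity, LLT use and attendance frequency (Appendix, Clinical effectiveness analysis and Study data). Clinic-recorded adherence is a newly added item (Section 6.1.1), so it may be absent for earlier patients.

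**The case against.** **This belongs in a statistical analysis plan.** Response weights for a nested survey are often left there, and that plan is not shown. This would settle the matter if the protocol were silent. But Section 7.5 names its method and Section 7.1 lists the components. A plan that followed them as written need not reach families who never join.

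**Costs do have weighting and imputation.** A reader might infer that the cost analysis has none. The text does not support that: the Objective 1(a) approach is carried over. With linked records, a child without a questionnaire could even be treated as having missing cost data. The protocol neither says so nor rules it out, so the gap is one of stated scope.

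**Other sources limit the harm.** A reader might infer that cost rests on volunteers alone. It does not. Healthcare professionals' questionnaires also feed resource use, CPRD holds GP attendance and hospital admissions, and Section 7.6 plans a scenario with guideline-based costs. These partly limit the harm. None of them corrects the patient-level estimate used in the main analysis.

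**Adherence is largely protected.** The GEE covariates overlap with the variables one would weight on, so the association estimates are partly covered. Adherence is also recorded in clinic across the Register and in CPRD. The model's parameter, the proportion on treatment at 18, comes from CPRD, so a claim that volunteer bias enters the model by that route would be wrong. What remains exposed is the descriptive level of self-reported adherence.

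**Denominator and size are uncertain.** Both points stand, which is why ranges are given. The protocol does not say whether the 613 existing patients can be invited.

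**Conclusion.** The point holds as a gap in the stated scope of the analysis, worth correcting. The patient-questionnaire cost estimate and the descriptive self-reported adherence level rest on a doubly self-selected group, about a third of the target Register and perhaps 53-66% of those who can be invited. No stated step is said to bring the results back to the Register population.

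The size is conditional. With 10-30% more appointments among joiners, mean use is overstated by about 6-17% at 36% participation, 7-20% at 29% and 3-9% at 66%. With no difference it is not overstated at all. The effect of LLT on cost is biased less if the extra use is a similar absolute amount in treated and untreated children. No single percentage should be read as an estimate of bias in this study: the protocol gives no joiner/non-joiner difference, and its direction is also assumed.

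**What to change.** In Sections 7.3 (analysis b) and 7.5, state that the Objective 1(a) approach extends to questionnaire participation and to response at each of the four waves:

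- Define the base population as Register patients who could be invited, and say whether it includes the existing 613.
- Estimate inverse-probability-of-participation weights in that population from linked Register variables: age, site, deprivation, ethnicity, LLT status, attendance frequency, and clinic-recorded adherence where available.
- Tabulate joiners against non-joiners on these variables.
- Report weighted and unweighted adherence and cost.
- Use the weighted cost in the economic model and the unweighted cost as a scenario.

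This needs no new data collection. The cost is a little more analysis and somewhat wider intervals. The weights correct only for differences that the Register variables capture.

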6.1.6 Participant commitment and data collection

Commitment for clinical data collection requires consent/assent on one occasion by the participant individual with FH and/or their parent/guardian. The clinical data collection period does not require any time commitment from the participant as data collection is done by clinical sites. Data collection will use routinely recorded information obtained during the course of clinical care from specialist clinic appointments. The REDCap secure web application will be used for clinical data entry to the PFHR.

Commitment for questionnaire data collection by the participant with FH and/or their parent/guardian is 2-3 years (based on time to return questionnaires), completing questionnaires on 4 different occasions, aimed at baseline, 8,16, and 24 months. Questionnaire data will be collected using REDCap web-based software or paper questionnaires.

Commitment for interview data collection by the participant with FH and/or their parent/guardian is one interview of up to 1 hour. Interviews will be conducted via telephone or Microsoft Teams and will be recorded using a handheld digital audio recorder. For interviews conducted online using Microsoft Teams, the transcription utility will be used to transcribe the interview without the use of audio-visual recording; the audio recording will be retained as a backup for listening to any sections of the interview where the text transcription file is unclear.

6.1.7 Participant withdrawal

Participants with FH aged 16 years and older or parents/guardians of a participant who is under age 16 may withdraw from further data collection. The participants will be made aware from the outset that this will not affect their current or future healthcare. Participants will be made aware (via information sheets and consent forms) that should they withdraw, the data collected to date cannot be erased from any research where it has already been used. As consent for the Register's clinical, questionnaire and interview data collection are separate, it will be possible for participants to withdraw from one aspect of the study whilst maintaining participation in another (e.g., withdrawal from interview but still participate in clinical data collection).

Clinical site staff participating in clinical data collection may not withdraw a participant without the consent of the participant or their parent/guardian.

6.2 The Clinical Practice Research Database (CPRD) paediatric FH cohort

CPRD RDG Protocol ID: 22-002278

The CPRD will be used as a secondary source of data to assess LLT treatment and potential sideeffects in children with FH, as well as medication adherence. This provides detailed longitudinal electronic health records from primary care with linkages to hospital admissions (but no access to specialist lipid clinic records). The general population in CPRD is highly representative of the sociodemographic distribution across the UK.¹¹ Our current unpublished research using CYP in the general population shows good national representation across socioeconomic and ethnic groups. Our June 2021 feasibility assessment of all CYP with diagnostic codes for FH in the CPRD GOLD database (which contains ~27% of the CPRD general population) showed they had a mean diagnosis age of 11 years, mean active follow-up 9 years, 64% were prescribed statins before age 18, and the mean number of LDL-C measures was 3, with almost half (42%) having prospective clinical records into adulthood. Using the whole of CPRD (GOLD and Aurum), we estimate at least 2,000 CYP with coded FH and another 1,600 with the clinical phenotype (based on our assessment of statin prescribing and hypercholesterolaemia coding). CPRD has reasonably complete information for these patients' gender, socioeconomic group, ethnicity, body mass index (BMI), however, it lacks the level of information on potential confounders that are available from the PFHR.

6.3 The Avon Longitudinal Study of Parents and Children (ALSPAC) cohort for deriving average cholesterol across childhood in the general (non-FH) population

ALSPAC Reference (B Number): B3815

The ALSPAC cohort will provide data for estimating average levels of LDL-C across childhood in the general (non-FH) population, a critical gap identified by clinical specialists and the NICE guidelines⁴ that needs addressing to inform FH treatment initiation and effective and safe target levels to which LDL-C should be reduced in CYP. ALSPAC is a longstanding cohort of children born in Avon in 1991-2 with repeated health and lifestyle measures into adulthood.¹² It is internationally unique in having repeated cholesterol and growth measures from birth to early adulthood. Cholesterol, growth and puberty measures are available at age 8,16,18 and 25 years (~7,000 CYP and ~2,000 with additional cholesterol near birth) as well as socioeconomic measurements, ethnicity and lifestyle factors that may be potential confounders. There are currently no other general-population British paediatric cohorts with such longitudinal measures.

